3.16.2. Clinical Laboratory Determinations

Blood and urine samples will be collected for testing the clinical laboratory parameters in Table 12 below at the time points outlined in the SoA.

Hematology	Biochemistry	Urinalysis	Other
Hemoglobin	Glucose	Glucose	TSH
Hematocrit	Sodium	Protein	HbA1c
Red blood cell	Potassium	Specific gravity	Human chorionic
White blood cell (WBC)	Calcium	pН	gonadotropin (hCG)
Platelets	Chloride	Ketones	(serum and urine pregnancy)
WBC Differential	Carbon dioxide (CO ₂)	Bilirubin	pregnancy)
	Inorganic phosphate	Urobilinogen	
	Blood urea nitrogen	Nitrite	
	Creatinine	Blood ^a	
	Creatinine clearance (estimated)	Leukocytes ^a	
	Aspartate transaminase (AST)		
	Alanine transaminase (ALT)		
	Gamma-glutamyl transferase (GGT)		
	Total bilirubin (TBL) (direct bilirubin reflex if elevated)		
	Albumin		
	Alkaline phosphatase (ALP)		
	Uric acid		

 Table 12:
 Clinical Safety Laboratory Parameters

^a Microscopic examination will be performed if blood or leukocytes are detected by dipstick.

Any clinically significant laboratory abnormality observed will be considered as an AE or SAE as appropriate.

3.16.3. Pregnancy Test

All female subjects of childbearing potential must have a negative pregnancy test at Screening to be enrolled in the study. Female subjects of childbearing potential will undergo a serum pregnancy test at the Screening Visit and urine pregnancy tests before injection on treatment visits (Day 1, 22 and 43).

3.16.4. Height and Weight

Height will be collected at screening only. Weight will be obtained at the Screening and Day 95/ET Visit.

Any clinically significant abnormality in weight compared to the screening value, will be considered as an AE or SAE as appropriate.

3.16.5. Vital Signs

Vital sign measurements will include systolic blood pressure (SBP), diastolic blood pressure (DBP), pulse rate, respiratory rate, and body temperature and will be taken at Screening, treatment visits (Day 1, 22 and 43), Day 64 and Day 95/ET Visits.

On days that study treatment is administered, vital signs will be taken up to 4 hours prior to dosing and at 15 and 30 minutes after dosing (body temperature is not required at the 15-minute

25-April-2022

post dose time point). The subject's vital signs must be stable, or repeated until stable, before the subject can leave direct observation.

Any clinically significant abnormality in vital signs observed will be considered as an AE or SAE as appropriate.

3.16.6. Electrocardiogram

A 12-lead ECG recording will be performed during the Screening Visit. The subject should be in a supine position for at least 5 minutes before the recording is conducted.

If the ECG report shows QT prolongation with $QTc \ge 450$ ms for males or $QTc \ge 470$ ms for females, the investigator will exclude the subject from study participation.

ECGs will be assessed by the Investigator and graded as:

- Normal.
- Abnormal, not clinically significant.
- Abnormal, clinically significant.

Any clinically significant abnormality in ECG observed will be considered as an AE or SAE as appropriate.

3.16.7. Physical Examination

The complete physical examination (by body system) on each subject will be performed at the Screening and Day 95/ET Visits. Physical examination will include: evaluation of the head, eyes, ears, nose, throat, neck (including thyroid), cardiovascular system (including assessment of heart, peripheral pulses, presence or absence of edema), lungs, abdomen (including liver and spleen, bowel sounds), lymph nodes, musculoskeletal system (including spine, joints, muscles), neurological system (including cranial nerves, reflexes, sensation, strength), skin, extremities, and other conditions of note.

The investigator will assess the physical examination findings as normal or abnormal. If physical examination findings meet the Investigator's criteria for clinical significance, then it will be reported as an AE or SAE as appropriate.

3.17. Immunogenicity

Immunogenicity variables include anti-AUX-I /anti-AUX-II binding antibodies (ie, anti-drug antibodies) and neutralizing antibody results. Serum samples will be collected at the Day 1 Visit (prior to study treatment administration) and at the Day 95/ET Visit for the determination of serum anti-AUX-I and anti-AUX-II antibody levels and neutralizing antibodies to AUX-I and AUX-II.

4. STUDY PARAMETERS

4.1. Subject Disposition

A subject will be considered to have completed the study if the subject has completed the Day 95 Visit.

Subjects who discontinue or are withdrawn from the study treatment for any reason will be encouraged to complete the remaining study visits and evaluations and provide any additional follow-up information as required by the study unless the subject specifically indicates that they will not participate in any further evaluations. The reason and date for study treatment discontinuation will be recorded in the eCRF.

If a subject withdraws from the study, all early termination procedures will be conducted as detailed in the SoA (Table 2). The reason and date for early withdrawal will be recorded in the eCRF for subjects who do not complete the study. If, however, a subject withdraws consent, no additional procedures are required except the collection of AE information. This information will be recorded in the source documentation and the eCRF.

Subjects who have been withdrawn from the study at any time after the first dose of study treatment will not be replaced. The reason for screen failure will also be recorded in the eCRF for subjects who consent to participate in this study but are not subsequently randomized.

4.2. **Protocol Deviations**

Potential deviations will be identified prior to database lock. Protocol deviations will be derived from the eCRF data, electronic vendor data and will be obtained from the clinical monitoring reports. All deviations from these sources will be reconciled and duplicate deviations will be removed.

Possible protocol deviations include, but are not restricted to the following deviation types:

- Ineligible subject/study entry criteria not satisfied.
- Informed consent not completed correctly.
- Non-compliance of study treatment.
- Prohibited medications/procedure.
- Visit/procedure missing or out of window.

The Endo study team will approve all final protocol deviation assignments and classify them as either major or minor during ongoing protocol deviation review meetings held throughout the study and a final meeting prior to the database lock.

4.3. Demographic and Baseline Characteristics

Demographics and baseline characteristics include the following parameters:

- Age.
- Height (at Screening).

- Weight (at Screening).
- Body Mass Index (BMI) in kg/m² (at Screening) (refer to Table 16).
- Gender.
- Race.
- Ethnicity.
- Time since last menstrual period for female subjects.
- Report of tobacco and alcohol use
 - Alcohol use (Never, Current, and Former).
 - Tobacco use (Never, Current, and Former).

4.4. Prior and Concomitant Medications

All medications will be coded using World Health Organization (WHO) Drug Dictionary, by active ingredient and WHO anatomical therapeutic chemical (ATC) classification of ingredients. The dictionary version to be used will be defined in the Data Management Plan (DMP).

A prior medication (or non-drug therapy) is defined as any medication (or non-drug therapy) taken prior to the Screening Visit and stopped before the Screening Visit.

A concomitant medication (or non-drug therapy) is any medication (or non-drug therapy) taken on or after the Screening Visit through the Day 95/ET Visit or taken prior to the Screening Visit and continuing during the study.

4.4.1. Prior Adhesive Capsulitis (AC) Treatment

Prior AC treatment will be obtained from the prior/concomitant medication and/or prior concomitant non-drug therapy pages of the eCRF. If on either of these pages a medication or nondrug therapy is reported with the indication 'Adhesive capsulitis' prior to the Screening Visit, then the medication or procedure will be considered a prior AC treatment.

All AC treatment medications will be classified as an "AC drug". All AC treatment procedures will also be classified. The classification will be reviewed and approved by the study medical monitor. Any AC treatment used after the Day 1 Visit will be noted and reported as a protocol deviation.

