6.5.1. Prohibited Medications and Nondrug Therapies

To be eligible for the study, subjects will agree not to use pain medications for the duration of the study period and for 2 weeks prior to the Screening Visit. Pain medications include, but are not limited to:

- opioids (eg, codeine, heroin, hydrocodone, hydromorphone, morphine, oxycodone, methadone, buprenorphine),
- cannabis.

Note: NSAIDs (ibuprofen, etc) and Tylenol (acetaminophen) are allowed.

In addition, the following medications or nondrug therapies will not be permitted during the study (from the Screening Visit through the Day 95 Visit):

- Anticoagulant or antiplatelet medication (except ≤ 150 mg aspirin daily).
- Any other medications or nondrug therapies for the affected shoulder other than those outlined in this protocol.
- Any collagenase treatments (eg, Santyl ointment, XIAFLEX) other than study treatment.
- Any investigational product, device, or procedure administered as part of a research study other than the treatment in this study.

If any prohibited medication/nondrug therapy is taken during the study, all pertinent information will be recorded. The designated study medical monitor must be informed immediately so the sponsor may determine whether to continue the subject in the study.

22 October 2021

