3.9. Prior and Concomitant Medications and Nondrug Therapies

Any medications and nondrug therapies (eg, blood transfusions, oxygen supplementation, physical therapy, etc) taken during the study or within 90 days prior to the Screening Visit will be recorded.

In addition, all prior medications and nondrug therapies for AC will be recorded.

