3.10. Prohibited Medications

To be eligible for the study, subjects will agree not to use pain medications for the duration of the study period and for 2 weeks prior to the Screening Visit. Pain medications include, but are not limited to:

- opioids (eg, codeine, heroin, hydrocodone, hydromorphone, morphine, oxycodone, methadone, buprenorphine),
- cannabis.

Note: NSAIDs (ibuprofen, etc) and Tylenol (acetaminophen) are allowed.

In addition, the following medications or nondrug therapies will not be permitted during the study (from the Screening Visit through the Day 95 Visit):

- Anticoagulant or antiplatelet medication (except ≤ 150 mg aspirin daily).
- Any other medications or nondrug therapies for the affected shoulder other than those outlined in this protocol.
- Any collagenase treatments (eg, Santyl ointment, XIAFLEX) other than study treatment.
- Any investigational product, device, or procedure administered as part of a research study other than the treatment in this study.

If any prohibited medication is taken during the study, all pertinent information will be recorded.

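### SAP 4.4.1 reports every adhesive-capsulitis treatment after Day 1 as a protocol deviation, with no exception for the analgesics and physical therapy that the plan itself permits or requires

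*SAP*

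**What the plan says.** SAP 4.4.1 works from the recorded indication. A medication or nondrug therapy entered for adhesive capsulitis "prior to the Screening Visit, then the medication or procedure will be considered a prior AC treatment". All AC medications are then labelled as an AC drug, AC procedures are classified too, and "The classification will be reviewed and approved by the study medical monitor". The section closes with the deviation rule: "Any AC treatment used after the Day 1 Visit will be noted and reported as a protocol deviation".

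SAP 3.10, repeating Protocol 6.5.1, first bars pain medications such as opioids and cannabis and then adds: "Note: NSAIDs (ibuprofen, etc) and Tylenol (acetaminophen) are allowed". Protocol 5.1 (criterion 2) and SAP 3.2.1 carry the same allowance. Protocol 6.5.1 goes on to say that "the following medications or nondrug therapies will not be permitted during the study (from the Screening Visit through the Day 95 Visit"), and its list includes "Any other medications or nondrug therapies for the affected shoulder other than those outlined in this protocol".

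SAP 4.2 separately lists "Prohibited medications/procedure" among the possible deviation types, with no starting day. SAP 3.9 says what is to be recorded: "Any medications and nondrug therapies (eg, blood transfusions, oxygen supplementation, physical therapy, etc) taken during the study".

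**The concern.** The same record can be compliant under one section of the SAP and a deviation under another. Ibuprofen entered for frozen shoulder on Day 30 falls within the allowance in SAP 3.10, yet 4.4.1 makes it a deviation because the rule covers any AC treatment. Supervised physical therapy is required of every subject (Protocol 8, SAP 3.13), and SAP 3.9 names physical therapy as a nondrug therapy to be recorded. If a site enters the study sessions there with AC as the indication, 4.4.1 flags those as well.

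Two outputs are exposed. The first is the deviation summary (SAP 7.2), which could report permitted conduct as non-compliance. The second is the Per-Protocol (PP) Population. The study team classes each deviation as major or minor, and SAP 4.2 gives no criteria for doing so. Pain makes up half of the adapted ASES composite (SAP 4.7.1.3), so analgesic use for AC could be argued to bear on the primary endpoint. If permitted use were classed that way, compliant subjects would leave the PP set for something that reflects their pain after randomisation.

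**Working it through.** The plan gives no figure to reproduce. The check is a comparison of the sections, followed by the one piece of arithmetic that bears on size.

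**Scope of treatments**
- SAP 4.4.1: any AC treatment, no exception. The only identification rule it supplies is the recorded indication.
- SAP 3.10 and Protocol 6.5.1: NSAIDs and acetaminophen allowed; shoulder therapies barred only if the protocol does not provide for them.
- Protocol 8 and SAP 3.13–3.14: supervised physical therapy and home exercise required of all subjects.
- Result: 4.4.1 covers more than the prohibition does. The excess is permitted or mandated treatment that carries AC as its indication.

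**Time window**
- SAP 3.10 and Protocol 6.5.1: Screening Visit through Day 95 Visit.
- SAP 4.4.1: after the Day 1 Visit.
- Difference: the screening period (up to 28 days) plus Day 1 itself.
- Other sections reach that interval. SAP 4.4 classes anything taken on or after Screening as concomitant, and the deviation types in SAP 4.2 have no Day 1 limit. The difference is one of wording between sections.

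**Was the broader scope intended?** SAP Table 17 lists the significant changes from the protocol: the PP definition and the tipping-point analysis. It does not mention a wider definition of prohibited AC treatment.

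**Route from a flag to an analysis**
1. A record is flagged under 4.4.1.
2. The study team classes the deviation as major or minor (SAP 4.2).
3. A subject leaves the PP set only for a major deviation that materially affects the primary endpoint (SAP Table 15).
4. If more than 10% of mITT is excluded, select efficacy summaries are repeated on the PP set as supportive analysis (SAP 7.9.5.1).

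The efficacy analyses in SAP 7.9, including the primary, use mITT and do not depend on any of these steps.

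**Size of the trigger**
- mITT of 142: 10% = 0.10 × 142 = 14.2, so at least 15 exclusions are needed.
- mITT of 180: 10% = 0.10 × 180 = 18, so at least 19 are needed.

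**Illustration only.** Analgesic use for AC is not stated, so 20% to 60% is assumed:
- Flagged: 0.20 × 180 = 36 to 0.60 × 180 = 108 subjects.
- If half of the flags led to PP exclusion: 18 to 54. The low end, 18, is exactly 10% of 180 and does not exceed the trigger; the high end does.

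**The case against.** The documents can be read as keeping pain medication and treatment for AC apart. The NSAID allowance sits with pain medication. Exclusion criterion 2 illustrates AC treatment with physical therapy, acupuncture, injections, nerve blocks, manipulation and surgery, and lists no oral analgesic. On that reading ibuprofen is not AC treatment unless a site enters AC as its indication, and the medical monitor's review could then reclassify it. Study physical therapy has its own listing (SAP 7.11.2) and may never reach the nondrug-therapy page.

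This limits how often the conflict would arise but does not remove it. The indication is the only test that 4.4.1 gives, and an analgesic taken for a frozen shoulder may well be entered under that diagnosis. Nothing tells the monitor to exempt permitted drugs, so a discretionary step would have to override an explicit rule.

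A reader might also infer that the SAP misses prohibited treatment given between Screening and Day 1. The documents do not support that. Section 4.4.1 says that use after Day 1 is a deviation; it does not say that earlier use is not. SAP 3.10 restates the full window, SAP 4.4 counts such use as concomitant, and the prohibited-medication and entry-criteria types in SAP 4.2 can capture it.

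**Conclusion.** The contradiction over scope is real and minor. Taken literally, SAP 4.4.1 reports as deviations some treatments that SAP 3.10 and Protocol 6.5.1 permit. This depends on how sites record the indication and on what the medical monitor does with it. The direct effect is on deviation counts; an effect on PP membership is possible but needs two further judgements by the study team. The mITT primary analysis does not change.

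It would go too far to infer that the 10% trigger will be met or that the PP set will be distorted. The usage range is an assumption, half of its low end does not exceed the trigger, and nothing in the SAP uses the AC drug label to decide PP membership. The textual conflict stands without those figures.

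**What to change.** Reconcile the last sentence of SAP 4.4.1 with SAP 3.10, SAP 4.2 and Protocol 6.5.1. One wording that sets no new clinical rule is: *AC treatment that is not permitted under Section 3.10 and protocol Section 6.5.1, used within the window stated there (Screening Visit through Day 95 Visit), will be reported as a protocol deviation of the prohibited medication/procedure type.* Add that study-mandated physical therapy and home exercise are not counted as AC treatment for this purpose. The window reference only brings the sections into line.

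Make the change before the final deviation review that precedes database lock. The cost is one or two sentences and a small recoding of the deviation derivation; no new data are needed.

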4.5. Passive External Rotation at 0°, 45°, and 90° of Abduction

Degrees and percent deficit of the affected shoulder compared to the contralateral shoulder will be calculated as:

Let

PS: Measurement from affected shoulder

PC: Measurement from contralateral unaffected shoulder

then

Degrees deficit = PS - PC

Percent deficit = (PS - PC) / PC) * 100

4.6. Home Exercise Compliance

The compliance to home exercise will be calculated as:

Compliance (%) = (No. of days with at least 2 home exercises / total number of days required home exercises) * 100

In-office physical therapy will count as 1 of the home exercise sessions when attended and completed.

4.7. Efficacy Parameters

4.7.1. Adapted American Shoulder and Elbow Surgeons Standardized Shoulder Form (ASES)

4.7.1.1. Pain Subscale

The adapted ASES pain subscale score is calculated as:

Pain subscale score = (10 - Pain Raw score) * 5

The score range for pain subscale is 0-50 representing the worst pain (0) to no pain (50).

Change from baseline in the adapted ASES pain subscale for the affected shoulder at the Day 22, 43, 64, and 95 Visits will be analyzed.

4.7.1.2. Function Subscale

The adapted ASES function subscale score is calculated by multiplying the total score for 10 items by 5 and then dividing it by 3. The calculation is:

Function subscale score = [(Sum of scores of 10 items) * 5]/3

If the responses to 1 or 2 items in the ASES function subscale are missing, the ASES function subscale score will be calculated as = $10 \times$ (mean of the scores for the non-missing activity items) \times 5/3. If more than 2 items of the responses to the ASES function subscale are missing, then the ASES function subscale score will be considered as missing.

The score range for function subscale is 0-50 representing no function (0) to full function (50).

Change from baseline in the adapted ASES function subscale for the affected shoulder at the Day 22, 43, 64, and 95 Visits will be analyzed.

4.7.1.3. Composite Score

The adapted ASES composite score is the sum of the pain subscale score (50% of the composite score) and the function subscale score (50% of the composite score). The calculation is:

Composite score = Pain subscale score + Function subscale score

25-April-2022

The range for the composite score is 0-100, where 0 is the worst pain and least functional and 100 is least pain and most functional. If either of the pain subscale or function subscale score is missing, then the ASES composite score will be considered as missing.

Change from baseline in the adapted ASES composite score for the affected shoulder at the Day 22, 43, 64, and 95 Visits will be analyzed. Positive change from baseline score means an improvement in pain and/or shoulder function from baseline.

4.7.2. Passive Range of Motion (PROM) and Active Range of Motion (AROM)

The PROM and AROM in affected shoulder at Day 22, 43, 64 and 95 will be analyzed for the following motions:

- Forward flexion.
- Internal Rotation.
- External rotation.
- Abduction.
- Shoulder extension.

The PROM and AROM will be analyzed at Day 22, 43, 64 and 95 using the following endpoints:

- Absolute change from baseline in affected shoulder
- Absolute and percent change from baseline in affected shoulder compared to the contralateral shoulder. The calculation is as below:

Let

ASi: Measurement from affected shoulder at visit i

CS1: Measurement from contralateral unaffected shoulder at baseline

then

Di = ASi - CS1

D1 (Baseline value) = AS1 - CS1

Absolute change = Di - D1

Percent change from baseline at Visit i = ((Di - D1) / D1) * 100

In addition, the HBB values will be ordinal ranked based on the level a subject can reach behind the back. The higher ranked assessment value signifies the ability to reach higher up behind the back. The lower the ranked value signifies the ability to reach behind the back low. A value of 0 will be assigned to subjects that cannot reach behind the back at all (the lowest rank possible).

The observed and change from baseline in HBB values will be analyzed at the Day 22, 43, 64 and 95 Visits.

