3.1.2. Schedule of Activities

 Table 2 below describes the schedule of events and assessments performed during the Screening Visit, Treatment visits, and Follow-up visits.

Table 2:Schedule of Activities

	eening Visit -28 to Day -1	Treatmen Da	t Session 1 iy 1	ession 1 L L + Ság		Treatment Day 22 + an Treatment Day 43 +	ys 25-28 and Days 46-49	vs 29-42 and ays 50-63	w-up Day 64 ± 5 days)	f Study Day 95 days)/Early vrmination	
Activity	Sc1 Day	Pre- injection	Post- injection			Pre- injection	Post- injection	Day	Da	Follo	End o (± 5 T
Informed consent ^c	X										
Inclusion/exclusion criteria review	Х										
Demography	Х										
Medical and surgical history	Х										
AC history	Х										
Prior medications and nondrug therapies	Х	Х									
Complete physical examination	X										Х
Height	Х										
Weight	Х										Х
Hand dominance	X										
Vital signs (blood pressure, respiratory rate, pulse rate, body temperature)	Х	Xd	X ^d			X ^d	X ^d			Х	Х
12-lead ECG	X										
Adapted ASES of the affected shoulder ^e	Xe	X				Х				Х	Х
Confirm external rotation ^f	Xe										
Passive external rotation at 0°, 45°, and 90° of the affected shoulder	Xe										
AROM and PROM of the contralateral shoulder	X										
AROM and PROM of the affected shoulder ^g	X					Х				Х	Х

	Lecuing Visit - 28 to Day -1 Day 1		Days 4-7	Days 8-21	Treatment Day 22 + an Treatment Day 43 +	Session 2 ^a 3 days ^b d Session 3 ^a 3 days ^b	ys 25-28 and Days 46-49	ys 29-42 and Days 50-63	ow-up Day 64 (± 5 days)	f Study Day 95 5 days)/Early ermination	
Activity	Sc Day	Pre- injection	Post- injection			Pre- injection	Post- injection	Da	Da	Foll	End e (±: T
PUM Assessment of the affected shoulder	Х	X								Х	Х
Patient-reported Global Severity of Adhesive Capsulitis ^e	Х	X				Х				Х	Х
Patient-reported Change in Severity of Adhesive Capsulitis ^e						Х				Х	Х
Chemistry, hematology, urinalysis, HbA1c, TSH, serum pregnancy test	Х										X^{h}
Urine pregnancy test		X				Х					
Immunogenicity sample collection		X									Х
X-ray of affected shoulder	Xi										
MRI of affected shoulder	Х										Х
MRI of unaffected shoulder	Х										
Randomization		X									
Ultrasound-guided study treatment injection and screen capture/photo of injection		X				Х					
Supervised in-office PT ^j					Х				Х		
Train subjects on home exercise and diary use, distribute home exercise instructions and diary			X					Х			
Home exercises ^k				2	K					X	

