3.4. Dose Interruption

All eligible subjects will receive their first dose of study treatment on Day 1. At each subsequent treatment visit (the Day 22 and 43 Visits) each subject will be evaluated to determine if they can continue treatment.

Subjects that have all 5 measurements of AROM and PROM (forward flexion, internal rotation, external rotation, abduction, and shoulder extension) of the affected shoulder that are > 90% of the baseline contralateral shoulder ROM and have an adapted ASES function subscale score of > 40 in the affected shoulder should not be dosed unless the investigator believes that the clinical benefit outweighs the risk.

Subjects who are not treated at the Day 22 Visit will continue in the study and will be reassessed at the Day 43 Visit and may be treated based on these assessments and investigator discretion. Subjects who are not treated at the Day 22 and/or Day 43 Visits will complete all other activities required for those visits and are also expected to complete the Day 64 and Day 95 Visits.

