6. STATISTICAL METHODS

6.1. General Methodology

All statistical tests, summary tables and data listings will be prepared using SAS version 9.3 or higher.

All statistical tests of efficacy parameters will be 2-sided with a significance level of α =0.05, unless specified otherwise. Statistical tests will be supported by presenting estimates and 95% confidence intervals (CI) for each treatment group.

Continuous data will be summarized using descriptive statistics (number of subjects [n], mean, SD, median, minimum, and maximum). Discrete data will be summarized using frequency counts and percentages. The denominator will be based on the number of subjects in the appropriate population.

For the purpose of display, the summary results will be rounded as follows:

- Minimum and maximum: Same number of decimal places as the raw data.
- Mean and Median: One more decimal place than the raw data.

- SD: Two more decimal places than the raw data.
- Percentages will be displayed with 1 decimal place precision. A zero count will be left blank.
- The standard form of a percentage change variable is 0 decimal places.

For categorical variables with missing values, a category documenting the frequency of missing values will be displayed in the summary tables.

Summary tables, subject listings, graphs and any supportive SAS output will include footnotes that will indicate:

- Date of data extraction.
- Date and time of output generation.
- SAS program name, including the path that generated the output.

When calculating percentages, the denominator will be based on the number of subjects with non-missing values. If the denominator is expected to change over time, then the denominator used to calculate the percentage will be based on the number of subjects with non-missing values at each visit. Any subject removed from an analysis will be noted at the bottom of the table along with the reason the subject was removed.

Empty summary tables will be presented with a note stating that "No Subjects Met Criteria."

Subject listings of all data from the eCRFs as well as any derived variables will be presented.

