6.3. Handling of Missing Data

Subjects who withdraw from the study after the initiation of the study drug will not be replaced and available data for these subjects until the point of withdrawal will be summarized.

Any missing baseline assessments (last assessment prior to initial study drug treatment) will not be imputed.

For categorical variables with missing values, a category documenting the frequency of missing values will be displayed in the summary tables.

25-April-2022

Subjects who withdraw early from study will be encouraged to have all EOS procedures and assessments completed at an early termination visit.

For ASES function subscale, if the responses to 1 or 2 items are missing, the ASES function subscale score will be calculated as = $10 \times$ (mean of the scores for the non-missing activity items) \times 5/3. If more than 2 items of the responses to the ASES function subscale are missing, then the ASES function subscale score will be considered as missing. If either of the pain subscale or function subscale score is missing, then the ASES composite score will be considered as missing.

There will be no imputation of missing values for safety data, however missing relationship between AE and study drug will be considered as related to study drug following worst case principle. Missing severity of an AE will be summarized as a severe AE. Duration of an AE will be classified in the "> 21 Days" category if an AE is ongoing for more than 21 days by the time of the last visit of the subject in the study.

Immunogenicity samples with a positive titer value will undergo a log transformation for analyses. Samples with titer level less than 10 will be assigned or imputed as a log transformed titer of 1 for analyses.

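### SAP 4.7.2 divides the contralateral-referenced percent ROM change by the baseline deficit and gives no rule for a zero, positive or very small deficit

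*SAP*

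**What the plan says.** SAP 4.7.2 takes AS as the affected-shoulder measurement and CS1 as the contralateral measurement at baseline, with D1 = AS1 - CS1 and Di = ASi - CS1. It then gives two contralateral-referenced quantities: "Absolute change = Di - D1" and "Percent change from baseline at Visit i = ((Di - D1) / D1) * 100".

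SAP 7.9.2.1 (PROM) and 7.9.2.2 (AROM) put both into an MMRM for five motions at Days 22, 43, 64 and 95, with LS means, 95% CIs and p values. PROM and AROM are the first two secondary objectives in Protocol 3.1.

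The rules that come nearest to the problem are these:

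- SAP 6.1: "Any subject removed from an analysis will be noted at the bottom of the table along with the reason the subject was removed". It also sets the display rounding of percentage changes.
- SAP 6.3: "Any missing baseline assessments (last assessment prior to initial study drug treatment) will not be imputed".
- SAP 4.7.2, for the hand-behind-back ranking only: "A value of 0 will be assigned to subjects that cannot reach behind the back at all".

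Elsewhere the SAP uses a different denominator. For passive external rotation at screening, SAP 4.5 divides by the contralateral value: "Percent deficit = (PS - PC) / PC) * 100".

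**The concern.** A percent change normally divides by a quantity that is positive and well away from zero. Here the divisor is the difference between two shoulders, which can be zero, small or of either sign. The formula works as a percent change in deficit when D1 is clearly negative, and improvement then appears as a negative number. Outside that range it fails in three ways: no value exists at D1 = 0, the sign of an improvement flips at D1 > 0, and a degree or two of deficit turns ordinary measurement error into hundreds of percent.

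The existing rules do not reach this. A footnote on removed subjects would disclose a loss at D1 = 0. With a positive or tiny D1 a number is computed and enters the model, so nobody is removed. The missing-baseline rule does not apply, because the baselines are present.

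At stake is the precision of one secondary expression of ROM. Without a rule, awkward values may also be handled after the data are seen.

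**Working it through.** **1. Algebra.** Di - D1 = (ASi - CS1) - (AS1 - CS1) = ASi - AS1, so the percent is 100(ASi - AS1)/(AS1 - CS1). CS1 cancels from the absolute change, which therefore equals the plain change in the affected shoulder. That is a redundancy, not a bias.

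**2. Same gain, different D1.** Take CS1 = 60 and a 10-degree gain (illustrative values).

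| AS1 | D1 | SAP percent | 100(ASi - AS1)/CS1 |
|---|---|---|---|
| 58 | -2 | -500% | +16.7% |
| 59 | -1 | -1000% | +16.7% |
| 60 | 0 | undefined | +16.7% |
| 61 | +1 | +1000% | +16.7% |
| 62 | +2 | +500% | +16.7% |

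**3. Which denominators are exposed.** 5 motions x PROM/AROM = 10 baseline denominators. Protocol 5.1 item 3 sets a numeric deficit (at least 30%) for passive external rotation only. Active external rotation is unlikely to be near zero given that passive loss. That leaves 10 - 2 = 8. Each is used at four visits, giving 8 x 4 = 32 of the 10 x 4 = 40 percent comparisons, but D1 does not change between visits.

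**4. Measurement error.** Assume the true gain is 60% of the deficit, with an error of 5 degrees either way: 100(0.6|D1| ± 5)/D1.

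| D1 | Range |
|---|---|
| -20 | -85% to -35% |
| -10 | -110% to -10% |
| -5 | -160% to +40% |
| -2 | -310% to +190% |
| -1 | -560% to +440% |

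**5. One such value in an arm.** The plan gives no figure for this endpoint. Its 142 subjects give 71 per arm, and that figure reproduces: a two-sample t calculation with difference 38.6 - 27.6 = 11.0, SD 21.6, two-sided 0.05 and 85% power needs 70.2, so 71 per arm. Assume the other 70 values average -60% with SD 40.

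- Mean: (70 x -60 - 310)/71 = -63.5, a shift of 3.5 points.
- SD: sqrt((69 x 40² + (70/71) x 250²)/70) = 49.6.
- SE of the arm difference: sqrt((49.6² + 40²)/71) = 7.56, against 40 x sqrt(2/71) = 6.71, a rise of 13%. At SD 30 the rise is 22%, and at SD 60 it is 6%.

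The mean hardly moves; the standard error does.

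**6. Power under continuous deficits (simulation, all inputs assumed).** 71 per arm, a Day 95 Welch test in place of the MMRM, and CS1 = 50. Gain is proportional to the deficit: recovered fraction mean 0.65 against 0.45, SD 0.35, clipped to -0.5 to 1.2, with no true gain if D1 > 0. Error SD is 5 degrees. Deficits are in whole degrees, with D1 = 0 dropped under the SAP formula. The exclusion rule keeps D1 <= -0.10 x 50 = -5.

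| D1 mean/SD | SAP formula | Exclusion rule (share excluded) | CS1 denominator |
|---|---|---|---|
| -20/10 | 38% | 64% (6%) | 60% |
| -15/8 | 27% | 53% (9%) | 51% |
| -10/6 | 16% | 38% (18%) | 38% |

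A rerun agreed within about two points.

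**The case against.** The strongest reply is that this rarely happens and matters little. Protocol 2.2 defines adhesive capsulitis by restriction of both active and passive motion. Protocol 4.1 requires unilateral disease with restricted ROM, and 5.1 requires an unaffected contralateral shoulder and an adapted ASES function score below 35. All of this pushes D1 negative. The absolute-change MMRM covers every motion and visit, and no document ties a decision to the percent result. The direction label could also sit in the table footnotes of SAP Module 2, which is not among the documents.

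Most of this stands, and it limits the point. It does not remove it, because none of these criteria sets a per-motion limit and the formula as written still produces a value when D1 is positive or tiny.

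A reader might infer more than the documents support:

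- **That the ROM analyses are invalid or alpha is inflated.** The absolute-change models do not use D1 as a divisor, and the illustrated cost is lost power, not false positives.
- **That 32 comparisons are separately exposed.** They rest on 8 baseline denominators.
- **That a minimum-deficit rule restores full power.** If most deficits are assumed to lie between -35 and -10 degrees and 1% to 5% of subjects are placed at ±1 or ±2, the rule holds 73% to 75% while the SAP formula falls from 75% to 28%. That near-full recovery depends on nobody lying between -10 and -2. The continuous table above shows a smaller gain.
- **That the SAP formula costs nothing when no deficit is near zero.** That holds only if gain is proportional to the deficit. If gain is unrelated to it, the formula has about 64% power against about 77% for the CS1 denominator.

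**Conclusion.** The point holds as a gap in a secondary derivation and should be fixed. The formula is undefined, wrong-signed or extreme for zero, positive or small D1. No rule in SAP 4.7.2, 6.1 to 6.3, 7.9.2.1, 7.9.2.2 or Table 17, or in Protocol 9.3.1, deals with these cases.

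The algebra and the count of 8 denominators come from the documents, apart from the judgement that active external rotation is unlikely to be near zero. The size of the effect does not come from the documents. How often D1 is zero, positive or small is not given, so every power and standard-error figure illustrates assumed distributions. The direction is consistent: where deficits reach zero, the SAP formula is the least precise of the three options tried.

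The consequence is lost precision and some wrong-signed values in the percent ROM endpoint. The primary ASES analysis, the sample size, alpha and the absolute-change ROM models are unaffected.

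**What to change.** Before database lock and unblinding, in SAP 4.7.2:

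1. Keep the formula and state that a negative percent means improvement.
2. For each motion, include in the percent MMRM only subjects with a pre-specified minimum baseline deficit, for example D1 <= -0.10 x CS1. The figure echoes SAP 3.4 ("90% of the baseline contralateral shoulder ROM"), but there it is part of a joint condition over all motions plus function. This would be a new per-motion use, as an analysis rule only, with no bearing on dosing.
3. Report the number excluded per arm and motion, and record in Table 17 that these are motion-specific subsets of mITT.
4. State that the contralateral-referenced absolute change equals the plain change.

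The Schedule of Activities in SAP 3.1.2 places "AROM and PROM of the contralateral shoulder" at Screening, along with the baseline ROM of the affected shoulder. Randomisation is on Day 1, so the rule uses pre-randomisation data and the arms stay comparable. Excluded subjects remain in the absolute-change MMRM.

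Downsides: the percent result then applies only to shoulders restricted in that motion, and retained deficits near the cut stay noisy (see D1 = -5 in step 4).

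The alternative is 100(ASi - AS1)/CS1, the contralateral denominator of SAP 4.5. It keeps every subject with CS1 > 0, and positive means improvement. It changes the estimand from the share of the deficit recovered to gain relative to the other shoulder.

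Cost: a few sentences in 4.7.2, cross-references in 7.9.2.1 and 7.9.2.2, a Table 17 entry and one baseline flag per motion. No new data are needed.
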